Risk Management Procedures. To guard confidentiality, only the participant's identification number will appear on questionnaires, and paper-based records, forms, and data will be kept in secure file cabinets. Computer records are protected by standard measures that limit access to the data to selected research project personnel. To reduce fatigue, the time needed to complete the cognitive and behavioral interviews will be minimized by thoroughly familiarizing the interviewers with the contents of the questionnaires. Our interviewers are trained not to press participants to answer questions that seem to be excessively distressing to them, and interviews will be terminated if the participant is too distressed, too fatigued, or too frustrated by the effort. Psychologists or psychiatrists will be consulted and will make an assessment in the event: (1) that an individual becomes distressed during the course of the interviews; (2) that the Beck

Depression Inventory score is greater than or equal to 12; or (4) that suicidal ideas are endorsed on the Beck assessments. Community referrals will be made when appropriate.

Subjects will be given information about the range of subjective effects they may experience from smoking marijuana, as well as relaxation techniques if the subjective effects of the marijuana are in any way disturbing or disorienting. Throughout the study the subject's health status as well as the general effects of the ingestion of cannabis will be monitored. Any adverse reactions will be reported immediately to the monitoring physician, the local IRB, and the Research Advisory Panel. This policy will be made explicit to all staff personnel, with the appropriate names, addresses, and telephone numbers of all relevant parties provided and posted.

Potential Benefits. Participants may benefit from participation by experiencing relief from their spasticity. The long term benefits from the study stem from a greater understanding of how cannabis affects spasticity in multiple sclerosis, and how it affects neuropsychological function and cognition.

Risk Benefit Ratio. The risk-benefit ration is low, since the participants will be carefully screened and followed and the importance of the knowledge gathered about the safety and effectiveness of cannabis should be significant.

Expense to Subject. None, other than time and effort taken.

Payment to Subject. No specific payments to subjects will be made for participation; however, if subjects need financial support with transportation or child care while they are participating in this project, funds will be available.

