Thirty persons with MS will be randomized to either placebo or smoked cannabis. Patients will be assessed before and after treatment for 3 consecutive days (phase I); undergo wash out for a total of 11 days; and then cross over to either placebo or active treatment (phase II) depending on what they received during Phase I. Since each phase of treatment requires 2 assessments (before and after inhaled product) on each of 3 consecutive days, the study will allow comparisons to be made on spasticity, cognitive, neuropsychiatric, safety and global measures before and after treatment with cannabis or placebo for a total of twelve assessments. Blood will be drawn for quantitative analysis of serum THC before and immediately following each treatment session as an estimate of systemic exposure.

Considering start-up time, training and recruitment of personnel, procurement of equipment and supplies, and unanticipated initial delays, we expect that one-third (n=10) of the required subjects will be recruited and tested during the first year and that the remaining two-thirds (n=20) of the required subjects will be recruited and tested during the second year of the study.

The following schedule of visits is planned:

	Screening I	Screening II	PHASE I Treatment Days 1-3		Washout (Days 4-14)	PHASE II Treatment Days 15-17	
			B	A		B	A
Consent	x						
Eligibility Checklist	x	x					
Medical Hx/Screens	x						
Concomitant meds	x	x					
Urine Toxicology	x		x#			x#	x#
Adverse Events			x	x		x	x
EDSS		x					
Modified Ashworth Scale	x	x	x	x		x	x
Timed 25-ft Walk		x	x	x		x	x
Pain Analog Scale			x	x		x	x
Cognitive Battery		x	x	x		x	x
Neuropsychiatric Assessment		x	x	x		x	x
Tx Emergent Effects				x			x
MSQLI			x†	x†		x†	x†
Practice Session		x					
THC Assays			x	x		x	x

B=before treatment; A=after treatment; †=Days 1, 3 and 15, 17 only; #= Days 1,15, and 17 only

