Patients will take no treatment for the next eleven days and will return to the CRC to begin Phase II on **Day #15**. A positive toxicologic screen for drugs of abuse other than cannabis will exclude the patient from further participation. (A positive urine toxicologic screen for cannabis and a peak plasma THC concentration greater than Day #3 will suggest illicit use and exclude the patient from further participation.) The Modified Ashworth Spasticity Scale, Spasm Frequency Score, Timed 25-ft Walk, Visual Analog Scale of Pain, cognitive battery, neuropsychiatric assessments, and MSQL-I will be administered. Blood will be drawn for total THC. Patients will undergo treatment with smoked product and blood will be drawn for peak THC levels. Patients will be assessed on the Modified Ashworth Spasticity Scale, Timed 25-ft Walk, Visual Analog Scale of Pain, cognitive battery, neuropsychiatric assessments, and treatment-emergent effects, beginning 30 minutes after their treatment session. Patients will return to the CRC at approximately the same time of day on **Day #16**. Blood will be drawn for total THC. Patients will be assessed on the Modified Ashworth Spasticity Scale, Timed 25-ft Walk, Visual Analog Scale of Pain, cognitive battery, and neuropsychiatric assessments. Following treatment with smoked product, blood will be drawn for peak THC levels and patients will again be assessed on the Modified Ashworth

Appendix to: [name], [name], [name], et al. Smoked cannabis for spasticity in multiple sclerosis: a randomized, placebo-controlled trial. *CMAJ* 2012. DOI:10.1503/cmaj110837.

Copyright © 2012 Canadian Medical Association or its licensors

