Spasticity Scale, Timed 25-ft Walk, Visual Analog Scale of Pain, cognitive battery, neuropsychiatric assessments, and treatment-emergent effects, beginning 30 minutes after their treatment session. On the last day of the protocol, **Day #17**, the patients will return to the CRC for their third treatment of Phase II. Blood will be drawn for total THC. Patients will undergo assessment with the Modified Ashworth Spasticity Scale, Timed 25-ft Walk, Visual Analog Scale of Pain, cognitive battery, and neuropsychiatric assessments. Following completion of the third treatment, blood will be drawn for peak THC levels, and patients will be assessed with the Modified Ashworth Spasticity Scale, Timed 25-ft Walk, Visual Analog Scale of Pain, cognitive battery, neuropsychiatric assessments, treatment-emergent effects, and MSQL-I beginning 30 minutes after their treatment session.

2. Study Site

The study will be performed at the UCSD La Jolla Clinical Research Center. The CRC is a self-contained organized research unit that is fully staffed by nursing, dietary and core laboratory personnel to support the clinical research project described herein. A room will be equipped with a Tepco 750 smoke scrubber or a HEPA filter (BioSafety, RS 1000).

3. Subjects

We estimate that 30 subjects will be necessary (see Section 7) in this crossover design and therefore plan to enroll 36 MS subjects, expecting attrition of up to 6 subjects over the course of the study. MS patients will be obtained through the UCSD MS Clinic and/or the private practices of their neurologists. These patients will have received extensive neurological evaluation and represent a well-studied MS patient population. MS patients will be solicited by [name], and contacted for appointment by the Research Coordinator. Patients of all ethnic and racial backgrounds are eligible. Prior use of cannabis is not required. Patients will be allowed to continue other currently available treatments for spasticity other than benzodiazepines, if they have been on a stable dose of the medication for at least three months.

3.a. Inclusion Criteria

Subjects will be included if they:

- Have clinically definite or probable, laboratory-supported MS; are between the ages of 18-65

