During Screening visit II, all subjects will be given information about the range of subjective effects they may experience from smoking cannabis, as well as relaxation techniques if the subjective effects of the cannabis are in any way disturbing or disorienting. Participants will be trained in the smoking procedure in a practice session during this visit. Under supervision of staff each participant will be exposed to one placebo cigarette using the Foltin Puff Procedure, and ratings will be recorded regarding the subjective and physical effects of cannabis (eg, UKU Side Effects Rating Scale, BSI). Staff will observe participants until the effects have abated.

During the actual experimental conditions, subjects will be assessed at the same time of day to regulate food, medication, and time of cannabis intake. The placebo and cannabis conditions will be administered by having subjects smoke one placebo or cannabis cigarette using the Foltin Puff Procedure. The cannabis cigarettes will contain 4% THC by weight; the placebo cigarettes will be constructed from the same base material but with the THC removed. The selection of the 4% THC cigarette is based on the strength of cannabis cigarette available from NIDA that most closely approximates the strength available in the community. Both placebo and cannabis cigarettes will be smoked in the fully equipped, ventilated smoking room at the UCSD La Jolla CRC. After smoking, subjects will have blood drawn for peak THC levels (two minutes after the last puff) and exhaled carbon monoxide measured for smoke exposure. Plasma THC levels will be measured as the most direct way to estimate systemic exposure. Plasma concentrations of THC are also expected to best predict physiologic response.

Subjects will remain in the laboratory under direct observation by Staff for 2 hours after the cannabis procedures are completed. At that time a final vital sign and self-report status check will be made and upon satisfactory readings, the subject will be released and driven back to his domicile by taxi cab or prearranged transportation. The return transport procedure also will be observed directly by staff to ensure compliance. Any serious adverse reactions will be reported immediately to the monitoring physician, the local IRB, and the Research Advisory Panel. This policy will be made explicit to all staff personnel, with the appropriate names, addresses, and telephone numbers of all relevant parties provided and posted.

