A total of 30 individuals will be enrolled over a two-year period. Individuals will be recruited as participants based upon specific medical and treatment characteristics, detailed previously as inclusion and exclusion criteria. All participants will be fully informed by trained personnel regarding the potential risks and benefits of participating in medical research. The purpose of the research, the schedule of visits, and the procedures to be performed will be fully explained. Participants will be informed that they may discontinue participation at any time and that discontinuation will not affect their future medical care. This information is also provided in a written document. After reviewing this document and asking any questions, the participant is asked to sign, indicating an awareness of the study requirements and a desire to take part in the research study. This consent is witnessed and is signed by medically competent personnel. The participant receives a copy of his/her signed consent forms (containing a name and contact number in case of emergency) and the original form is retained. The participant also receives a copy of "The Experimental Subject's Bill of Rights".

Potential Risks. Potential risks of data collection in this study include mental and/or emotional distress that may result from questions asked during assessment or as a result of the time taken in the assessment process. In addition, some neuropsychological tests may require concentrated effort and may be frustrating to the participant to complete. There are no potential physical risks posed by neurobehavioral examinations. Standard risk is associated with venipuncture include pain, bruising, and a very low risk of infection. Risks of inhaled cannabis products may include psychomotor coordination difficulties, eye irritation, throat irritation, increased heart rate, possible hypotension, reversible appetite/mood/memory/cognition effects. Smoking marijuana may prejudice application for future employment, if drug screening is a condition of employment. It is likely that detectable traces of marijuana will remain in the hair or blood for a minimum of six weeks after smoking.

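### No adverse-event enquiry is scheduled the day after the third dose of either phase: after Day 3 the next is 12 days later, and after release on Day 17 there is none.

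*Protocol*

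**What the plan says.** The schedule of visits in Protocol section D.1 has a row headed "Adverse Events". It is marked in the before and after columns of Phase I (Days 1-3) and of Phase II (Days 15-17). The key reads "B=before treatment; A=after treatment", so enquiry is tied to session days. The washout cell (Days 4-14) is blank and there is no column after Phase II. The treatment-emergent scales are marked only after smoking.

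The narrative in D.1 agrees with the table. Of the washout it says: "Patients will take no treatment for the next eleven days and will return to the CRC to begin Phase II on" Day 15. Day 17 is named as the end of the protocol, and on it "patients will return to the CRC for their third treatment of Phase II". The exit urine screen listed in D.7 falls on Day 17 by the schedule's footnote, so it does not imply a later visit.

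On what follows a session, D.5 says: "Subjects will remain in the laboratory under direct observation by Staff for 2 hours after the cannabis procedures are completed". A last check of vital signs and self-reported state then precedes release and observed transport home. Vital signs under D.6 also stop at 2 hours.

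Section E states under Risk Management Procedures: "Throughout the study the subject's health status as well as the general effects of the ingestion of cannabis will be monitored". It gives no time point or contact after release. Under Potential Risks it lists "reversible appetite/mood/memory/cognition effects" among the possible effects. The consent paragraph of section E says that patients receive a contact number for emergencies.

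**The concern.** The Overview says that short-term safety, above all neuropsychiatric safety, will be emphasised, and Aim 2 is about acute and short-term tolerability. D.4 gives accurate estimation of side effects as one reason for the placebo control. An event that begins at home after the 2-hour observation can be recorded systematically only if someone later asks about it. For the first two doses of a phase the enquiry before the next day's session does this.

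The third dose follows the most exposure within a phase and is the one with no such enquiry. Depending on sequence, the period after the last cannabis dose is asked about 12 days later, when recall is poorer, or is not asked about at all. At stake are the completeness of the absolute counts of delayed events and a missed safety contact after the full three-day course. The visit schedule belongs to the protocol, so this is not a detail that an SAP would be expected to supply.

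**Working it through.** **Inputs**
- Session days: 1, 2, 3, 15, 16, 17 (D.1).
- Assessments: "each phase of treatment requires 2 assessments (before and after inhaled product) on each of 3 consecutive days" (D.1).
- Patients: 30 required, 36 to be enrolled, up to 6 expected to be lost (D.3).
- Allocation ratio: not stated. Assumed 1:1, with a range of 10 to 20 of 30 patients receiving cannabis second.

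**The plan's own figure.** 2 assessments x 3 days x 2 phases = 12, which matches the twelve assessments stated in D.1. The schedule has therefore been read as intended.

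**Gap from each dose to the next scheduled enquiry** (next session day minus dose day)

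| Dose on | Next scheduled enquiry | Gap |
|---|---|---|
| Day 1 | before session, Day 2 | 1 day |
| Day 2 | before session, Day 3 | 1 day |
| Day 3 | before session, Day 15 | 15 - 3 = 12 days |
| Day 15 | before session, Day 16 | 1 day |
| Day 16 | before session, Day 17 | 1 day |
| Day 17 | none | - |

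**Cannabis doses affected, 30 completers.** Total: 30 x 3 = 90.
- Next-day enquiry: 30 x 2 = 60 of 90 (67%).
- No next-day enquiry: 30 x 1 = 30 of 90 (33%). Each completer has exactly one third cannabis dose, on Day 3 or Day 17, so this share does not depend on the ratio.
- At 1:1, Day 3 doses with the next enquiry 12 days later: 15 of 90 (17%).
- At 1:1, Day 17 doses with no later enquiry: 15 of 90 (17%).

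**Range for doses with no later enquiry**
- 10 of 30 receive cannabis second: 10/90 = 11.1%.
- 20 of 30 receive cannabis second: 20/90 = 22.2%.
- 36 patients, 18 per sequence, none lost: 18/108 = 16.7%, with 36/108 = 33.3% lacking next-day enquiry.
- 36 patients start, 18 per sequence, and all 6 losses are placebo-first patients before Phase II: 18 x 3 + 12 x 3 = 90 doses, and 12/90 = 13.3%.

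**Comparison between products.** At 1:1 the third placebo doses split in the same way: 15 on Day 3 and 15 on Day 17. The pooled pattern of enquiry is then identical for the two products. Within a patient it is not. A placebo-first patient is asked on Day 15 about the time since the last placebo dose but is never asked about the time after the last cannabis dose; for a cannabis-first patient it is the reverse. If the sequences were unequal, this would not cancel: with 10 of 30 receiving cannabis second, 10/90 cannabis doses (11%) and 20/90 placebo doses (22%) would have no later enquiry.

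The protocol gives no rate for events that first appear after release, so the number of events missed cannot be estimated.

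**The case against.** The strongest reply is that safeguards exist and that the protocol does not contradict itself. Patients are observed for 2 hours, released only when readings are satisfactory, and escorted to transport. They hold an emergency number, and section E requires adverse reactions to be reported at once. All of this stands. It means that the gap is in scheduled enquiry, not in every route of reporting. It does not close the gap, because an emergency number yields only what the patient chooses to volunteer.

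Two stronger readings are tempting, and the documents do not support them.

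- A reader might infer that the monitoring promise in section E ("Throughout the study the subject's health status as well as the general effects of the ingestion of cannabis will be monitored") is contradicted by the schedule. That sentence closely follows the purpose D.6 gives for the vital signs taken around each session, and it is naturally read as describing that session monitoring. Since Day 17 ends the protocol, the absence of a later contact cannot contradict a statement about the study period. At most there is some tension over Days 4-14.
- A reader might infer that reversibility of mood, memory and cognition effects goes unchecked in patients who receive cannabis second. Those patients repeat the cognitive battery and neuropsychiatric assessment before smoking on Days 16 and 17, about a day after their first and second cannabis doses. Only the third dose lacks this. The word reversible also stands in a list of possible risks and is not a result that the trial undertakes to test.

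It can also be said that an enquiry after washout already exists, since adverse events are marked before the Day 15 session. That is correct. The change needed there is only to state which period it covers.

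**Conclusion.** The gap is real but limited to the third dose of each phase. With 30 completers, 30 of 90 cannabis doses have no scheduled next-day enquiry, and this holds for any allocation ratio. The share with no later scheduled enquiry is 15 of 90 (17%) under an assumed 1:1 split, or 11% to 22% if 10 to 20 of 30 patients receive cannabis second.

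The consequence is that absolute counts of delayed events may be too low and that a useful safety contact is missed. Under-counting is possible but not shown, for want of any rate of delayed events. A reader might go further and infer that the comparison of side effects between cannabis and placebo is biased. With balanced sequences the pooled comparison is not, because placebo doses have the same gap. The primary efficacy analysis is untouched. The change is worth making because short-term safety is a declared emphasis and the repair is cheap.

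**What to change.** The change concerns data collection only. Dosing, the observation period and the release rule stay as written.

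1. Add a scripted adverse-event telephone contact the day after the last dose of each phase (Day 4 and Day 18), with identical wording for both products.
2. For a patient who leaves early, make the same call the day after the last cigarette smoked.
3. State that the existing enquiry before the Day 15 session covers Days 4-14.
4. Mark these contacts in the schedule of visits, and state the adverse-event collection period, for example from the first cigarette to the Day 18 contact.

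This brings cannabis doses without next-day enquiry from 30 of 90 to 0 of 90. The cost is about 2 x 30 = 60 to 2 x 36 = 72 short calls by existing staff, somewhat more events to record, and one extra day of follow-up.

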necessary. Unfortunately, many patients suffer sufficient side-effects from these medications to preclude their use at potentially effective doses. For others, severe spasticity may persist despite adequate dosing. Baclofen has been associated with elevated liver enzymes and typical side effects include drowsiness, fatigue, weakness, nausea, and dizziness. Side effects of benzodiazepines include sedation and cognitive impairment, in addition to the potential for dependence. Tizanidine has been associated with dry mouth (45%), drowsiness (54%), dizziness (19%), blood pressure effects, visual hallucinations, and elevated liver enzymes. Thus, for individuals with MS, spasticity remains a significant medical problem that does not, at present, have a wholly satisfactory treatment.

Studies of cannabinoids for spasticity in MS have had mixed results but clinical studies have been small, generally not properly controlled, with results controversial, and difficult to interpret. A report of the first questionnaire on cannabis use and MS in 53 UK and 59 US MS patients described improvement in spasticity, chronic pain of the extremities, acute paroxysmal phenomenon, and tremor with smoked cannabis (Consroe et al, 1997). Open label evaluations of oral cannabinoids in small mixed populations of subjects have reported significant reductions in spasticity (Petro and Ellenberger, 1981; Meinck et al, 1989) and dystonia by clinical measurement (Consroe et al, 1986).

Recently, investigators in the UK and US tested the ability of cannabinoids to control spasticity and tremor symptoms of the MS-like disease, experimental allergic encephalomyelitis, in mice (Baker et al, 2000). The authors found that four different cannabinoids quantitatively ameliorated both tremor and spasticity in diseased mice; thus, providing a rationale for patients' reports of the therapeutic effects of cannabis in the control of their MS symptoms.

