Treatment Emergent Effects of cannabis will be assessed after each treatment by interview and self-report of physical and psychological symptoms using the Subjective Ratings of High and Sedation - Revised (SRHS-R) and the UKU Side Effect Rating Scale. The **Subjective Ratings of High and Sedation - Revised** has been adapted from Block, et al (1998) for use in the present study to evaluate the subjective effects of cannabis. This scale consists of 10 ratings of different aspects of stimulation vs. sedation (alert/drowsy, attentive/dreamy, tense/relaxed, interested/bored, capable/incompetent, excited/calm, clear-headed/fuzzy, well-coordinated/clumsy, quick-witted/mentally slow, and energetic/lazy). The **UKU Side Effect Rating Scale** is a semi-structured interview that evaluates a wide range of unwanted side effects including psychological (eg, concentration difficulties, failing memory, lassitude), neurological (eg, hypokinesia, paraesthesias), autonomic (eg, accommodation disturbance, orthostatic dizziness, nausea, sweating), and miscellaneous effects (eg, weight gain, diminished sexual desire) (Lingjaerde et al 1986). Each treatment emergent symptom is defined on a four-point scale of intensity (0 = not present; 3 = severe), and rated separately with regard to being causally related to the study drug (improbably related, possibly related, probably related). In addition, sitting and standing blood pressure, heart rate, respirations, and oral temperature will be obtained before

Appendix to: [name], [name], [name], et al. Smoked cannabis for spasticity in multiple sclerosis: a randomized, placebo-controlled trial. *CMAJ* 2012. DOI:10.1503/cmaj110837.

Copyright © 2012 Canadian Medical Association or its licensors

drug administration and at 0.5, 1 and 2 hours after administration to monitor the subject's health status as well as to quantify cannabis's general effects.

Quality of Life (administered at the beginning and end of each phase):

The **Multiple Sclerosis Quality of Life-Inventory** is both a generic and an MS-specific quality of life measure (Coulthard-Morris, 2000). It consists of 138 items and 10 separate scales that assess the following domains: general health status, fatigue, pain, sexual satisfaction, bladder control, bowel control, vision, cognitive function, mental health, and social support. It is self-administered and takes about 30 minutes to complete.

7. Laboratory Assessments

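### No blood pressure or heart rate is scheduled between the end of smoking and 0.5 hours, so an early cardiovascular change would go unrecorded

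*Protocol*

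**What the plan says.** Section D.6 (Assessment Measures, treatment-emergent effects) provides that "sitting and standing blood pressure, heart rate, respirations, and oral temperature will be obtained before" and, as the sentence continues, "drug administration and at 0.5, 1 and 2 hours after administration to monitor the" patient's health. It gives these readings two purposes: safety monitoring, and a measurement purpose stated in the words "subject's health status as well as to quantify cannabis's general effects".

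Section D.5 (treatment conditions) fixes an earlier contact: after smoking, "subjects will have blood drawn for peak THC levels (two minutes after the last puff"), and exhaled carbon monoxide is measured as well. It adds: "Plasma concentrations of THC are also expected to best predict physiologic response". It also has staff watch the patient for two hours, with a last vital-sign check before release.

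Section E (Potential Risks) lists "increased heart rate, possible hypotension" among the risks of the inhaled product. Section B calls a faster heart rate a common physical effect. Section B also reports, for tizanidine, "blood pressure effects, visual hallucinations, and elevated liver enzymes"; section 3.a requires a stable dose of either baclofen or tizanidine.

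Section D.1 starts the post-treatment battery, which includes the Timed 25-ft Walk, 30 minutes after the session.

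**The concern.** The plan measures exposure at what it calls the peak but takes no cardiovascular reading at that contact or at any other time before 0.5 hours. Section D.4 justifies the placebo control partly by the need for accurate side-effect estimates, and the vital signs are meant to quantify an effect as well as to protect the patient. If heart rate rises or blood pressure falls early and then recovers, neither purpose is served for that interval, and the placebo sessions cannot supply what was never measured in the cannabis sessions.

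A second, smaller matter follows from the timing. The first standing blood pressure after smoking and the start of a battery that includes a timed walk both fall at about 30 minutes, and the protocol does not say which comes first.

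**Working it through.** The protocol states no figure for this point that could be reproduced. Its power statement in section D.8 does not enter, and nothing here changes it.

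**Inputs**
- Peak THC sample: 2 minutes after the last puff (D.5).
- First vital signs after dosing: 0.5 hours, or 30 minutes, after administration (D.6).
- Sessions: 3 days in each of 2 phases, one phase on cannabis (D.1).
- Patients: 30 (D.1).
- Puff cycle: 5 s inhalation, 10 s hold, 45 s wait (D.4).

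**Length of the interval between the THC sample and the first vital signs**
- Both clocks from the last puff: 30 − 2 = 28 minutes.
- If the 0.5 hours run from the first puff, the gap is 28 minutes less the smoking time. One cycle takes 5 + 10 + 45 = 60 seconds, so smoking takes about one minute per puff. The protocol does not give the number of puffs, so this shorter gap cannot be fixed from the document.

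**How often it occurs**
- 3 × 2 = 6 sessions per patient; 30 × 6 = 180 sessions in all; 30 × 3 = 90 on cannabis. This counts 30 patients completing both phases.

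**What the schedule can and cannot show**
- Write Δ(t) for the change from the pre-dose reading at time t after dosing. The recorded extreme is the largest of Δ(0.5), Δ(1) and Δ(2). Measurement error aside, it cannot exceed the true maximum of Δ(t). The two are equal only if the true maximum falls at one of the three reading times.
- The shortfall depends on the time course of heart rate and blood pressure after smoking. The protocol states none, so the shortfall has no computable size.

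**Passages side by side**
- D.5 links plasma THC to physiologic response but does not say that the two peak together.
- E names the cardiovascular risks but gives no time for them.
- D.6 sets the reading times and gives no reason for starting at 0.5 hours.
- D.1 and D.6 both place activity at about 30 minutes, one counted from the treatment session and the other from administration, without an order.

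**The case against.** A reader might infer that the protocol contradicts itself: plasma level predicts response, THC peaks at two minutes, so the cardiovascular effect must peak there and the schedule misses it. The documents do not support that. The sentence in D.5 justifies plasma THC as the exposure measure; it describes an association between concentration and response and says nothing of timing. If heart rate or blood pressure lags behind plasma THC, the 0.5-hour reading may capture the maximum. For the same reason it cannot be said that the readings are biased toward no effect, nor can a share of the missed change be given, since any such percentage would need a decay rate that the protocol does not state.

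Other points on that side also stand. Section D.8 names no cardiovascular endpoint, and comparisons of cannabis with placebo at matching times remain valid for those times. Starting at 0.5 hours fits the start of the other assessments. Safety in the gap is not left open: staff observe the patient directly for two hours, and the UKU interview after each treatment covers orthostatic dizziness. Patients on baclofen or tizanidine are on stable doses and serve as their own controls.

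It is also tempting to say that patients will walk before their standing pressure is known. The protocol does not put the walk first; it leaves the order unstated.

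These arguments limit the point but do not remove it. Observation and a symptom interview yield no blood pressure or heart rate values, so a change without symptoms in that interval would leave no record.

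**Conclusion.** The point holds as a gap in measurement. Between the end of smoking and 0.5 hours no blood pressure or heart rate is scheduled, in any of the 6 sessions per patient, although the readings are meant both to monitor safety and to quantify effects. An early maximum would go unrecorded, and the largest recorded change may understate the true maximum. Whether it does, and by how much, cannot be determined from the protocol. The 28-minute figure assumes that both clocks run from the last puff.

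The primary outcome, the sample size and the planned tests are unaffected. This is an inexpensive improvement to the safety data and not a flaw that threatens the trial's conclusions.

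**What to change.** - In section D.6, add a blood pressure and heart rate reading at the existing two-minute blood draw, in every cannabis and every placebo session, and keep the readings at 0.5, 1 and 2 hours. Pairing it with the draw also puts a cardiovascular value beside each peak THC level.
- State whether the vital-sign times count from the first or the last puff.
- Reconcile sections D.1 and D.6 on the order of the 0.5-hour vital signs and the Timed 25-ft Walk. Which order is right is for the investigators to decide; the protocol should state it.

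Cost: one short reading in each of 180 sessions, at a contact where blood is already drawn and exhaled carbon monoxide is also measured after smoking. No new visit or type of measurement is needed. The downside is a few busier minutes directly after smoking.
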